Comprehensive Analysis of Clinical Parameters that May Inform the Choice of Dose Regimen for Carfilzomib 20/27mg/m² or 20/56mg/m² With and Without Dexamethasone

- Study Background and Rationale

Prior attempts to evaluate different carfilzomib (K) and carfilzomib in combination with dexamethasone (Kd) dosing regimens demonstrated limitations of the collected data on clinical parameters and outcomes. The aim of this analysis is to pool data from Amgen-sponsored clinical trials to describe the benefit-risk profile of clinical parameters associated with efficacy and safety outcomes of subjects treated with one of four different dosing regimens to inform the choice of carfilzomib regimen. The dosing regimens of carfilzomib include a therapeutic dose of 27mg/m² or 56mg/m², each as monotherapy or in combination with dexamethasone (K27, K56, Kd27, Kd56).

- Study Feasibility and Futility Considerations

Upon initial review of Amgen-sponsored K clinical trials, there was a limited number of subjects receiving K56 (N=45 subjects). This does not allow a robust comparison of data from this regimen to data from the K27 regimen. Statistical models will be used to determine a favorable or unfavorable association of clinical parameters and choice of carfilzomib regimen.

- Research Question and Objectives

Objectives	Endpoints
Primary	

 • Describe the benefit-risk profile for each pre-specified K regimen (K27, Kd27, K56, Kd56) based on the clinical parameters that are associated with efficacy and safety outcomes from the pooled data meeting the criteria for sample size and completeness of covariates 	
 • Efficacy outcomes: Progression free survival (PFS) and Objective Response • Safety outcomes: 
 ○ Grade 3 or higher adverse events and Serious Adverse Events (SAE) for the following key risks that may impact the overall benefit risk profile of carfilzomib: 
 ▪ Cardiac failure (SMQN) ▪ Acute Renal failure (SMQN) ▪ Hypertension (SMQN) ▪ Cardiac events [totaling the incidence using cardiac failure (SMQN), ischaemic heart disease (SMQN), torsades des pointes including QT prolongation (SMQN)] ○ Fatal adverse events
Secondary	

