7.6.2 Review and Verification of Data Quality

The database of each individual clinical trial was subject to edit checks outlined in the data management plan. Data inconsistencies and suspicious values were reviewed and resolved before the database was locked for analyses in clinical study report. The analysis datasets and variables in each individual clinical trial had been validated by sponsor. In this pooled study, each individual trial will follow its own derivations of the endpoints and variables, which are specified in its own SAP.

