7.7.2.2 Missing or Incomplete Data

The descriptive statistics will identify the extent of missing data. Rules for handling incomplete or missing data related to endpoints are detailed in the SAP of each individual trial. For this analysis, no imputation will be done for the analysis of the safety endpoints and efficacy endpoints. The handling of incomplete or missing dates for adverse events and death are also detailed in the SAP of each individual trial. For this analysis, the missing values for the continuous clinical parameters, or covariates, will not be imputed. The missing values for categorical covariates in each individual trial will be classified into a category called Unknown.

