7.7.2.4 Analysis of the Primary, Secondary, and Exploratory Endpoint(s)

For the primary endpoint, the analyses will describe the distribution of each clinical parameter and the distribution of each efficacy/safety outcome by each dosing regimen (K27, Kd27, K56, and Kd56) to yield a summary of the favorable versus unfavorable effects for each dosing regimen.

For the secondary and exploratory endpoints, the outcomes for efficacy will use the well-established endpoints of PFS, an approved surrogate marker of overall survival, and ORR, one of the most commonly used endpoints in myeloma clinical trials. Each individual trial will follow its own definition of PFS and ORR, which was specified in its respective SAP, to derive these pooled data. For analyses of PFS, Kaplan-Meier estimates will be used to estimate the median and other quartiles along with corresponding two-sided 95% confidence intervals. For analyses of ORR, the associated 95% exact binomial confidence interval (Clopper-Pearson method) will be

reported for Kd56 versus Kd27 and Kd27 versus K27. Risk ratio (RR) with the corresponding 95% CIs for Kd56 versus Kd27 and Kd27 versus K27 will be estimated using Cochran-Mantel-Haenszel (CMH) method. To account for potential differences in drug exposure duration, exposure-adjusted incidence rate with the corresponding 95% CI will also be calculated.

Also, for the secondary and exploratory endpoints, outcomes for safety will use endpoints of all fatal events as well as grade 3 or higher and serious adverse events (AEs) of special interest (List 2). Classification of the severity of AEs from each trial will be in accordance with the NCI-CTCAE criteria used during that individual clinical trial, which was also specified in its respective SAP. The number and percentage of subjects experiencing the treatment-emergent adverse event (TEAE) by system organ class/preferred term (SOC/PT) will be summarized for the specified safety outcomes and presented side-by-side for the 4 dosing regimens (K27, K56, Kd27, Kd56) overall for both the primary and sensitivity analyses.

List 2. Adverse Events of Special Interest (in alphabetical order)

- Acute renal failure (SMQN)
- Cardiac events (Sum of events for cardiac failure [SMQN] + ischemic heart disease [SMQN] + torsades des points including QT prolongation [SMQB])
- Cardiac failure (SMQN)
- Hypertension (SMQN)

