7.7.3 Analysis of Safety Endpoint(s)/Outcome(s)

Please refer to [Section 7.7.2.4](#) for the description of the efficacy and safety analyses. The Medical Dictionary for Regulatory Activities (MedDRA) version 23.0 or later will be used to code all events.

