7.9.3 Limitations Due to Missing Data and/or Incomplete Data

As previously noted, the implementation of these studies spanned nearly a decade, whereby the understanding of the myeloma disease has greatly improved. Despite special consideration, data for particular variables in several clinical trials may not exist. For example, as the predictors for outcomes in MM remain complex, the data collection

for two cardiovascular parameters of tobacco exposure and family history of early coronary artery disease have be inconsistent and thus will be excluded. Also, given the recent recommendations for FISH analysis, there would be no data for this clinical parameter of chromosomal abnormalities in earlier years of clinical trials. With the anticipate large volume of unknown data, this clinical parameter will be excluded. These parameters have been excluded to avoid large volumes of empty data fields due to non-existent data that would jeopardize the integrity of the analyses. To address data that is missing (versus non-existent data), please see [Section 7.7.2.2](#).

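### Grade 3 or higher AE contrasts use each trial's own CTCAE criteria and, by the general derivation rule, its own treatment-emergent window; Kd27 and Kd56 share no trial, so any difference in either is inseparable from regimen

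*Protocol*

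**What the plan says.** The abstract's objectives table makes grade 3 or higher AEs and serious AEs for the key risks, together with "Fatal adverse events", the safety outcomes of the primary objective. The secondary (Kd27 versus Kd56) and exploratory (K27 versus Kd27) objectives use the same endpoints. Section 7.7.2.4 compares them by risk ratio after propensity score matching.

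Four rules decide how these events are measured:

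- **Severity** (Section 7.7.2.4): "Classification of the severity of AEs from each trial will be in accordance with the NCI-CTCAE criteria used during that individual clinical trial".
- **Derived variables** (Section 7.6.2, with similar text in Section 7.3.5): "each individual trial will follow its own derivations of the endpoints and variables, which are specified in its own SAP".
- **Unit of safety reporting** (Section 7.7.2.4): "The number and percentage of subjects experiencing the treatment-emergent adverse event (TEAE) by system organ class/preferred term (SOC/PT) will be summarized". The protocol gives no window for a treatment-emergent event.
- **Dates** (Section 7.7.2.2): "The handling of incomplete or missing dates for adverse events and death are also detailed in the SAP of each individual trial".

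Two things are common to all trials: the MedDRA dictionary (Section 7.7.3: "version 23.0 or later will be used to code all events") and the event groupings in List 2. On the age of the data, Section 7.9.3 says that "the implementation of these studies spanned nearly a decade".

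**The concern.** A common dictionary and common groupings make the event terms comparable. They do not make the grade comparable, nor the period after the last dose in which an event still counts. If those differ between trials, and if trials map one-to-one onto regimens, a difference in how outcomes were measured appears as a difference between doses.

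The study is descriptive, but its stated purpose is to inform the choice of carfilzomib regimen, and Section 11 sends the report to the FDA. A false dose-toxicity signal, or a real one hidden, would bear directly on that purpose.

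The protocol does not discuss the issue. The limitations in Section 7.9 cover confounding, loss of unmatched subjects, the small K56 group and missing data. The ENCePP checklist in Appendix A says information bias is addressed in Section 7.3.4, but that section only adds year of treatment initiation as a covariate. The checklist then marks control of outcome misclassification, and the impact of information bias, as not applicable.

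**Working it through.** **1. Reproduce the plan's group sizes (Tables 2 and 3).**

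- Primary Kd27: 235 + 123 + 20 + 205 = 583. Primary Kd56: 153 + 463 = 616. Together 1,199, as stated.
- Primary K27: 78 + 200 + 157 + 105 = 540, as stated.
- Sensitivity Kd27: 235 + 123 + 3 + 20 + 205 = 586. Sensitivity Kd56: 153 + 463 + 8 + 3 = 627. Both as stated.

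**2. Count the trials shared within each contrast.**

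| Contrast | Set | Shared trials | Share of each arm |
|---|---|---|---|
| Kd27 vs Kd56 | Primary (Table 2) | none | 0% and 0% |
| Kd27 vs Kd56 | Sensitivity (Table 3) | none | 0% and 0% |
| K27 vs Kd27 | Primary | 2011-002 | 105/540 = 19% and 205/583 = 35% |
| K27 vs Kd27 | Sensitivity | 2011-002, 20140122, 20140120 | 120/559 = 21% and 228/586 = 39% |

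For Kd27 versus Kd56, anything set at trial level is therefore also set at regimen level. K27 versus Kd27 is partly protected.

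**3. Ask whether a planned step removes the difference.**

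- Matching (Section 7.2.2) balances List 1 baseline covariates. It does not change how an outcome was graded or windowed. Year of treatment initiation is in List 1, but grading criteria are set by trial, so similar years do not ensure common criteria.
- The exposure-adjusted incidence rate (Section 7.7.2.4) addresses duration of exposure, not the grade 3 threshold.
- The sensitivity set adds 586 − 583 = 3 Kd27 and 627 − 616 = 11 Kd56 subjects, under the same rules.

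**4. Size, under assumptions.** The protocol gives no CTCAE version, window or event rate, so the share *s* and the risk *p* below are assumed. Suppose the true risk is equal in both arms, and a share *s* of the events that count as grade 3 or higher in one arm would fall below grade 3 under the other arm's criteria. Then

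apparent RR = 1 / (1 − s).

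For a confidence interval, take n = 583 per arm, the most pairs that 1:1 Kd27/Kd56 matching can give, with a = np and b = np(1 − s) events:

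SE(log RR) = √(1/a − 1/n + 1/b − 1/n), 95% CI = RR × exp(±1.96 SE).

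| s | Apparent RR | 95% CI, p = 5% | 95% CI, p = 10% | 95% CI, p = 15% |
|---|---|---|---|---|
| 10% | 1/0.9 = 1.11 | 0.66–1.86 | 0.78–1.58 | 0.84–1.47 |
| 20% | 1/0.8 = 1.25 | 0.73–2.13 | 0.87–1.81 | 0.93–1.68 |
| 30% | 1/0.7 = 1.43 | 0.82–2.49 | 0.97–2.10 | 1.05–1.94 |

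Worked case, p = 15%, s = 30%: a = 87.45, b = 61.2, SE = √(0.01144 + 0.01634 − 0.00343) = 0.156, and 1.43 × exp(±0.306) gives 1.05 to 1.94.

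With the arms reversed, the same shares give 0.90, 0.80 and 0.70, so a real excess could equally be hidden. The same formula serves for a window difference, with *s* the share of one arm's counted events that fall outside the other arm's shorter window.

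**The case against.** The strongest reply is that no difference has been shown. The protocol names no CTCAE version and no window for any trial. A span of nearly a decade makes different criteria plausible, but a reader who infers that the two regimens were in fact graded differently goes beyond the document. That stands, and the point is worded conditionally for this reason.

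Other parts of the reply also stand:

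- **Window.** A reader might infer that the protocol says each trial's treatment-emergent flag is carried over. It does not. This follows only from the general rule on derivations, and Section 7.7.2.4 refers further detail to SAP Sections 9.5 and 9.6, which may define one window.
- **Fatal AEs.** The grade 3 threshold does not affect whether an event was fatal. Only a window or date-handling difference can reach fatal AEs.
- **Serious AEs.** These are a parallel outcome that does not depend on CTCAE grade, so the output does offer one comparison free of the grading question.
- **Trial range.** No phase 1 trial is in the primary Kd contrast. Kd27 comes from two phase 3 trials, one phase 2 trial and the phase 2 expanded access programme; Kd56 comes from two phase 3 trials.
- **Precision.** Eight of the nine illustrative intervals include 1, and the study tests no hypothesis.

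What does not stand is that all of this is SAP detail. The severity rule and the rule on derivations are written into the protocol, and the lack of any shared Kd27/Kd56 trial is visible in its tables. Wide intervals do not remove bias in a point estimate that will be read descriptively.

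**Conclusion.** The concern holds in a limited form. The grade 3 or higher contrasts pool grades assigned under each trial's own criteria, by explicit rule. The treatment-emergent window is undefined in the protocol and, by the general rule, would also follow each trial. For Kd27 versus Kd56 any difference in either is inseparable from regimen; for K27 versus Kd27 it is diluted by shared trials, of which there is only one in the primary set.

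The size is not known from the document. A 10% to 30% shift across the grade 3 threshold would turn a true risk ratio of 1.00 into 1.11 to 1.43. This rests on equal true risk and an assumed shift affecting one whole arm. A shift in only some of that arm's trials would give less.

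A reader might also conclude that grade 3 or higher should give way to serious AEs in the safety summary. The protocol does not support this: grade 3 or higher is a stated outcome of the primary objective, and reading the two side by side is enough.

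**What to change.** - **One window.** Define a single treatment-emergent window for the pooled data, derive it from AE onset, death and first and last dose dates, and apply it to the List 2 events and fatal AEs. If the SAP already does this, say so in Section 7.7.2.4 and exempt it from the general rule in Sections 7.3.5 and 7.6.2.
- **Grading.** Tabulate the CTCAE version by trial. Where versions differ between arms, add a sensitivity analysis restricted to trials on the same version, if trials allow. Kd56 has only two primary-set trials, so this may be impossible; if so, report that.
- **Reading.** Keep grade 3 or higher as an outcome and present it beside the serious AE result for each List 2 event.
- **Limitations.** State in Section 7.9 that any remaining grading difference between Kd27 and Kd56 cannot be separated from dose, and correct the checklist entries on information bias and outcome misclassification.

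The cost is modest programming, one table and a few extra rows. First and last dose dates are already needed for duration of treatment (Section 7.7.2.3). Section 7.7.2.2 anticipates incomplete AE and death dates, so the window needs a stated rule for them. The downside is that late events outside the common window leave the comparison; they can stay in per-trial listings.

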
 • Compare efficacy and safety outcomes for K dosing regimens with dexamethasone (Kd27 versus Kd56) 	
 • Same efficacy and safety endpoints in the primary objective
Exploratory	

 • Compare efficacy and safety outcomes for K27 dosing regimens without and with dexamethasone (K27 versus Kd27) 	
 • Same efficacy and safety endpoints in the primary objective

- Hypothesis(es)/Estimation

No formal hypothesis testing is planned for the efficacy and safety comparison between K dosing regimens (Kd56 versus Kd27; Kd27 versus K27). All analyses will be descriptive.

- Study Design/Type

This is a retrospective, post-hoc, pooled analysis of interventional carfilzomib studies using internal data from Onyx-owned databases and the RAVE database, which is used for all clinical trials conducted by Amgen that span across the globe.

- Study Population or Data Resource

The study population is all subjects with relapsed or refractory relapsed multiple myeloma (RRMM) who received consistent twice-weekly K treatment with K27, Kd27, K56, or Kd56 via an Amgen-sponsored clinical trial.

- Summary of Eligibility Criteria

- Amgen acquired or sponsored clinical trial
- Clinical trial that enrolled subjects with RRMM
- Subjects treated with K administered as twice weekly in the following regimens: K27, Kd27, K56, or Kd56

- Variables

Selection of current treatments depend on a plethora of clinical parameters that vary in important and might affect the choice of K regimen for a particular patient. Given that the benefit-risk assessment is a cornerstone of decision making in medicine, and benefit-risk assessment is based upon efficacy outcomes and safety outcomes ([Reaney et al, 2019](#); [Curtin et al, 2011](#)), special consideration will be given to clinical parameters known to impact efficacy and safety outcomes in those treated with carfilzomib. Specified below are the clinical parameters for analysis ([List 1](#)) for efficacy outcomes such as progression-free survival (PFS) and objective response rate and safety outcomes such as fatalities, grade 3 or higher AEs of special interest for carfilzomib, and serious AEs of special interest for carfilzomib. Variables common to both efficacy and safety outcomes are listed first.

List 1. Planned Variables to be Analyzed that May Inform the Choice of Carfilzomib Dosing Regimen

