Clinical review for identification of AEs of special interest for this post-hoc analysis spanned the following types of events, in alphabetical order: cardiac, gastrointestinal, haematological (cytopenias), infusion reactions, peripheral neuropathy, pulmonary, renal, tumor lysis syndrome, and viral infections. Specific AEs of special interest consistently identified throughout the individual clinical trials were as follows (SMQNs unless otherwise specified): acute renal failure, cardiac arrhythmia, drug-related hepatic disorder, dyspnea (HL), embolic and thrombotic events – venous, hemorrhage, hepatic failure/fibrosis and cirrhosis/other liver damage-related conditions, hypertension, interstitial lung disease, ischemic heart disease (SMQB), liver related investigations - signs and symptoms, malignant or unspecified tumors, myocardial infarctions (SMQB), pulmonary hypertension, thrombocytopenia (SMQB), and torsade de pointes – QT prolongation (SMQB) (Carfilzomib Investigator's Brochure, 2019). However, AEs of special interest identified for this pooled analysis reflect the AEs of special interest consistently identified in individual clinical trials with increased incidence compared to

the control cohort without K or were notable in safety reports. This approach should capture AEs that lead to non-fatal treatment discontinuations for K, even if the overall incidence for that AE was low. Although thrombocytopenias occur in more than 20% of individuals treated with K, nearly all treatments for MM induce myelosuppression ([Package inserts for Cyclophosphamide, 2013](#); [Darzalex, 2016](#); [Empliciti, 2015](#); [Pomalyst, 2017](#); [Revlimid, 2017](#); [Sarclisa, 2020](#); [Thalomid, 2014](#); [Velcade 2008](#)) and supportive measures (eg platelet transfusions) are part of standard-of-care practices, making thrombocytopenia a less critical clinical parameter that may inform the choice of K dose in the RRMM setting. In other words, [List 2](#) focuses on those AEs that has the potential to directly impact the benefit-risk profile for K and thereby inform the choice of K dose regimen.

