For the secondary and exploratory endpoints, each propensity score analysis will compare the efficacy (Hazard Ratio (HR)(CI) for PFS and Odds Ratio (OR)(CI) for ORR) and safety outcomes (Risk Ratio (RR)(CI)) overall and in subgroups determined by the clinical parameters from [List 1](#) (covariates). Based on the results, the favorable versus unfavorable effects of Kd27 versus Kd56 and K27 versus Kd27 will be summarized. The comparison of K27 versus K56 will not be included due to the limited sample size of the K56 cohort.

For further details, please refer to Section 9.5 and 9.6 of the SAP.

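### The cardiac events composite has two conflicting definitions: torsades/QT is narrow in one place and broad in another, and both are worded as sums that do not fit subject-level reporting.

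*Protocol*

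**What the plan says.** The objectives and endpoints table in the Abstract (section 4) lists safety outcomes under the primary objective, as grade 3 or higher and as serious events. One of them is "Cardiac events [totaling the incidence using cardiac failure (SMQN), ischaemic heart disease (SMQN), torsades des pointes including QT prolongation (SMQN". All three component queries there carry the narrow-scope suffix.

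List 2 in section 7.7.2.4 defines the same outcome as "Cardiac events (Sum of events for cardiac failure [SMQN] + ischemic heart disease [SMQN] + torsades des points including QT prolongation [SMQB". Cardiac failure and ischemic heart disease stay narrow; torsades/QT becomes broad. The text after List 2, on events identified across the individual trials, also has "torsade de pointes – QT prolongation (SMQB". It gives "ischemic heart disease (SMQB" as well, although both definitions of the composite use the narrow query for that component.

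On reporting, section 7.7.2.4 states: "The number and percentage of subjects experiencing the treatment-emergent adverse event (TEAE) by system organ class/preferred term (SOC/PT) will be summarized". It plans risk ratios with 95% confidence intervals by the Cochran-Mantel-Haenszel method, and the propensity score comparisons are to give "safety outcomes (Risk Ratio (RR)(CI". For both the secondary and the exploratory objective the Abstract says "Same efficacy and safety endpoints in the primary objective", so the composite goes into both regimen comparisons.

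**The concern.** Cardiac toxicity is named among the key risks meant to inform the choice of regimen, so the composite must mean one thing. Two features of the text prevent that.

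First, the narrow and broad versions of a query are different term lists. A programmer working from the objectives table and one working from List 2 would flag different torsades/QT events, and so possibly different subjects.

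Second, a percentage of subjects and a risk ratio both need one yes/no result per subject. A total of three incidences, or a sum of events, is not that unless each subject is limited to one count, and neither definition says so. If the text were programmed literally, the reported figure would not be a risk, and the usual variance for a risk ratio would not apply to it.

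**Working it through.** **Step 1. The definitions side by side.**

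| Place in protocol | How combined | Cardiac failure | Ischemic heart disease | Torsades/QT |
|---|---|---|---|---|
| Abstract, objectives table | total of incidences | narrow | narrow | narrow |
| 7.7.2.4, List 2 | sum of events | narrow | narrow | broad |
| 7.7.2.4, text after List 2 (events identified in the individual trials) | not a composite | not listed | broad | broad |

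The first two rows are current definitions of the same outcome and differ in the torsades/QT scope. The text after List 2 says that its entries are narrow unless marked otherwise, so the suffix is used on purpose and carries meaning.

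The two definitions also describe different sums. Totalling three incidences can count a subject up to three times. Summing events can in addition count repeat events within one query.

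**Step 2. What a sum does to the level.** The protocol states no cardiac incidence, so there is no figure to reproduce. All rates below are assumptions chosen to show a range. Let p1, p2, p3 be the proportions of subjects with cardiac failure, ischemic heart disease and torsades/QT.

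- Sum: p1 + p2 + p3
- Subjects with at least one, components independent: 1 − (1 − p1)(1 − p2)(1 − p3)
- Subjects with at least one, full overlap: the largest of the three

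| Assumed p1 / p2 / p3 | Sum | Independent | Sum ÷ independent | Full overlap | Sum ÷ full overlap |
|---|---|---|---|---|---|
| 5% / 2% / 1% | 8.0% | 1 − 0.95 × 0.98 × 0.99 = 7.83% | 1.022 | 5.0% | 1.60 |
| 8% / 4% / 2% | 14.0% | 1 − 0.92 × 0.96 × 0.98 = 13.45% | 1.041 | 8.0% | 1.75 |
| 10% / 5% / 3% | 18.0% | 1 − 0.90 × 0.95 × 0.97 = 17.07% | 1.055 | 10.0% | 1.80 |

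The relative excess is about 2-6% under independence and 60-80% under full overlap.

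**Step 3. What a sum does to the ratio.** The sum equals the proportion of subjects affected times m, the mean number of component queries per affected subject. Hence the ratio of sums equals the subject-level risk ratio times (m in one regimen ÷ m in the other).

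- Same m in both regimens: the factor is 1 and the ratio is unchanged.
- Assume 10% of subjects are affected in both regimens, with no overlap in one. If 25% of affected subjects in the other have a second component, the ratio is (10% × 1.25) ÷ 10% = 1.25. At 50% it is (10% × 1.50) ÷ 10% = 1.50. The subject-level risk ratio is 1.00 in both cases.

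Nothing in the protocol says whether overlap differs between regimens, or by how much.

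**The case against.** The double-counting part depends on a literal reading. The sentence that sets the reporting unit stands just above List 2 and speaks of subjects, and the effect measure for safety is a risk ratio. Against that background, summing three queries can be read as pooling their term lists and then counting subjects. No passage says that a subject is to be counted more than once. Rules for deriving flags are commonly left to the SAP, to which section 7.7.2.4 refers for detail and which was not available here. This stands in part. It makes a once-per-subject count the plausible intention, but both definitions use additive wording and neither says so.

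It is also fair that all analyses are descriptive, that cardiac failure is a separate outcome untouched by either issue, and that the ratio is unaffected when overlap is alike. A descriptive risk ratio with a confidence interval still needs a defined numerator.

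A reader might go further and infer that the planned binomial intervals are invalid. The protocol does not support that: the exact binomial interval is assigned to objective response, and the Cochran-Mantel-Haenszel variance fails only if subjects really are counted repeatedly.

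The objection does not reach the scope conflict. Whichever scope the SAP adopts, it contradicts one of the two protocol definitions.

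**Conclusion.** The scope conflict is certain from the text: torsades/QT is narrow in the objectives table and broad in List 2, for the same outcome. The additive wording is also certain. That it leads to double counting is a consequence of reading it literally and is not an established plan.

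The size cannot be determined from the protocol. The 2-6% and 60-80% figures rest on assumed component rates and two extreme overlap patterns. The ratios of 1.25 and 1.50 rest on an assumed difference in overlap between regimens.

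Three stronger conclusions might be inferred and are not supported. One is that the cardiac rate or the Kd27 versus Kd56 ratio will be distorted; no rates or overlap are given. Another is that this is the primary endpoint; it is one of several safety outcomes under the primary objective. The third is that narrow scope is correct because the objectives table uses it. List 2 and the text after it both say broad. That text is only weak evidence for either side, because it describes the individual trials and also differs from List 2 on ischemic heart disease.

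**What to change.** Before analysis:

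1. State one torsades/QT scope, identically, in the objectives table and in List 2. The choice is the sponsor's, noting that List 2 and the text after it both say broad. Report the other scope as supportive.
2. Replace the additive wording in both places. Define cardiac events as subjects with at least one qualifying event in any of the three queries, each subject counted once, for grade 3 or higher events and separately for serious events.
3. Carry the same definition into the SAP and the two regimen comparisons.

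The cost is a few lines of text and one flag variable, with no new data. The stated incidence may come out slightly lower than a literal sum. Settling this beforehand also avoids choosing a definition after the results are known.
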